#### **Exploratory objectives:**

- 1. Explore mechanism of action and markers of response and resistance through assessment of baseline and on-treatment biopsies.
  - a. Evaluation of association between expression of MHC-I, MHC-II, B2M, PD-1, PD-L1, PD-L2, FoxP3, CD68, CD4, and CD8 by tumor cells and achievement of complete response to therapy will be assessed by Wilcoxon rank sum test. Due to the small sample size, the association between these biomarkers and PFS will be assessed descriptively by dichotomizing the biomarkers by median and generating Kaplan-Meier curves of PFS for each group and comparing them visually.
  - b. Molecular profiling of baseline and on-treatment biopsies and association with response will be assessed by Wilcoxon rank sum test. Due to the small sample size, the association between these biomarkers and PFS will be assessed descriptively by dichotomizing the biomarkers by median and generating Kaplan-Meier curves of PFS for each group and comparing them visually.
- 2. Evaluate plasma EBV PCR as a marker of response to therapy and/or early predictor of relapse. Associated between EBV DNA and response will be assessed using Wilcoxon rank sum test. Due to the small sample size, the association between this biomarker and PFS will be assessed descriptively by dichotomizing the biomarkers by median and generating Kaplan-Meier curves of PFS for each group and comparing them visually.

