#### 14.0 BIOSTATISTICS

#### **Primary objectives:**

The primary objective of this pilot study is to assess the complete response (CR) rate to pembrolizumab in untreated ENKTL following pembrolizumab. Patients who receive any number of cycles of pembrolizumab and undergo response assessment or come off study before response assessment for disease progression will be evaluable for response. CR will be defined as complete metabolic response or negative biopsy in the setting of residual PET avidity. Although there are marked differences in progression free survival for patients with early stage disease (stage I,II) versus advanced stage disease (stage III, IV), complete response rate to treatment (such as SMILE) is similar regardless of stage. Therefore, for the primary objective, early stage and advanced stage patients will be analyzed together. Early stage disease is more common and thus we expect that 66% of patients enrolled onto this study will have early stage disease. If pembrolizumab is efficacious in untreated ENKTL, the treatment approach evaluated in this study will be evaluated in a larger phase II study. Based

upon expression of PD-L1 in ENKTL and experience in the relapsed/refractory setting, we expect that the clinical or pathologic complete response rate to pembrolizumab in untreated disease will be at least 40%. We plan to enroll 19 patients with untreated ENKTL. Assuming a complete response rate of 40%, the 95% confidence interval with a sample size of 19 is 0.18-0.62, i.e. the width of the interval is 0.44. Patients who are removed prior to the first response evaluation will be counted as non-responders.

This study is expected to enroll 19 patients over 2 years.

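### Markers are related to PFS only through a median split compared by eye; for baseline markers a stage-stratified hazard ratio on the continuous scale, with an interval, would use the 19 patients better

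*Combined protocol and SAP*

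**What the plan says.** Section 14.0 (Biostatistics, Exploratory objectives) uses the same sentence for the tissue markers (item 1a), molecular profiling (item 1b) and plasma EBV DNA (item 2). Because the sample is small, association with PFS "will be assessed descriptively by dichotomizing the biomarkers by median and generating Kaplan-Meier curves of PFS for each group and comparing them visually". No hazard ratio, between-group difference or interval is planned for any marker against PFS.

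Item 1a covers ten markers: "expression of MHC-I, MHC-II, B2M, PD-1, PD-L1, PD-L2, FoxP3, CD68, CD4, and CD8 by tumor cells". Item 2 adds EBV DNA, with the aim to "Evaluate plasma EBV PCR as a marker of response to therapy and/or early predictor of relapse". That makes 11 markers before any molecular feature is counted.

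For response, the same section leaves the markers uncut: the association of the tissue markers with "achievement of complete response to therapy will be assessed by Wilcoxon rank sum test", and the same test is named for items 1b and 2.

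On size, the primary-objective text says "We plan to enroll 19 patients with untreated ENKTL". On stage mix, "we expect that 66% of patients enrolled onto this study will have early stage disease". The secondary-objective text counts PFS from the start of treatment and analyses it separately for early and advanced stage. The biomarker paragraphs do not repeat that separation.

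**The concern.** A small sample is where lost information costs most. Cutting a quantitative marker at its median treats values just either side of the cut as opposites, and the cut point itself is set by these 19 patients. Two curves of 9 and 10 patients, judged by eye, carry no measure of uncertainty between them. The plan did not need a cut to relate the same markers to response.

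At stake is what the trial hands on. The protocol foresees a larger phase II study, and the marker work is meant to inform which markers deserve attention there. Without an effect size and interval, a reader cannot tell a plausible lead from a chance gap between curves.

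**Working it through.** **1. The plan's own precision figure.** The only one concerns the complete response rate: "Assuming a complete response rate of 40%, the 95% confidence interval with a sample size of 19 is 0.18-0.62". A Wald interval gives 0.40 ± 1.96 × √(0.40 × 0.60 / 19) = 0.40 ± 0.22, that is 0.180 to 0.620. It reproduces. No precision, target effect or event count is given for the marker–PFS analysis, so event counts must be assumed.

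**2. Assumed events.** Inputs are the 66% early-stage share (about 13 early, 6 advanced) and the historical 2-year PFS in Section 3.0: 56% early and 18% advanced, or 83% for early-stage patients given SMILE. With exponential PFS, expected events by year T are Σ n × (1 − S^(T/2)), where S is 2-year PFS.
- T = 3, 56%/18%: 13 × (1 − 0.56^1.5) + 6 × (1 − 0.18^1.5) = 7.55 + 5.54 = 13.1
- T = 3, 83%/18%: 3.17 + 5.54 = 8.7
- T = 2, exact 66/34 mix: 12.54 × 0.44 + 6.46 × 0.82 = 10.8, or 12.54 × 0.17 + 6.46 × 0.82 = 7.4

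A working range is 7 to 13 events.

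**3. Information kept by the split.** For a normal marker, the squared correlation between the value and its above-median indicator is 2/π = 0.637, and 19 × 0.637 = 12.1 patients. In simulation with 2-year censoring the split kept 55% to 62%.

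**4. Power, as a measure of that loss.** Cox score tests, two-sided 5%, normal marker, n = 19. The hazard ratios are assumptions, because the plan gives none.

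| Setting | HR per SD | Full scale | Median split |
|---|---|---|---|
| 56%/18%, 3 years, about 13 events | 2.0 | 52% | 36% |
| 83%/18%, 3 years, about 9 events | 2.0 | 26% | 18% |
| one pooled PFS rate, 2 years, about 11 events | 2.0 | 54% | 36% |
| one pooled PFS rate, 2 years, about 8 events | 2.0 | 44% | 29% |
| one pooled PFS rate, 2 years, about 11 events | 1.5 | 24% | 18% |
| one pooled PFS rate, 2 years, about 8 events | 1.5 | 18% | 13% |

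In the 56%/18% setting at HR 2.0, stratifying by stage gives 52% against 34%. Using ranks gives 47%, so most of the gain does not depend on the marker's scale. With a threshold effect instead (HR 3 above the population median, 56%/18%), the split is slightly better: 33% against 30%.

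**5. Precision of what could be reported.** With d events, the approximate 95% limits of a per-SD hazard ratio are the estimate multiplied and divided by exp(1.96/√d): 2.10 at d = 7, 1.81 at d = 11 and exp(1.96/3.606) = 1.72 at d = 13. These are wide.

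**6. What the eye would see by chance.** Treating 2-year PFS as a simple proportion of about 43%, the 95% half-width for a difference between halves is 1.96 × √(0.43 × 0.57 × (1/9 + 1/10)) = 0.446, or about 45 points. With no true association, the halves differ by 30 points or more in about 16% of trials. Across 11 markers taken as independent, 1 − 0.84^11 = 0.85 is the chance of at least one such gap. Correlation between markers would lower it.

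**7. Stage.** Suppose a marker runs 1 SD higher in advanced disease and has no effect within stage. An unstratified full-scale test then rejects in 25% of trials (83%/18%) or 12% (56%/18%), and the unstratified split in 18% or 10%. A stage-stratified full-scale test rejects in about 6%.

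**The case against.** The strongest reply is that this is a choice of method, not an error. Section 14.0 labels the analysis exploratory and descriptive (although Section 2.0 lists the marker aims among the secondary objectives). No test or alpha is attached, so the power figures compare two tests that are not planned. This stands: the figures measure how much information is lost and do not show that a planned test fails. The markers are also analysed uncut against response, so only the PFS part is affected. That stands too.

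The advantage of the full scale rests on a roughly continuous marker and a log-linear effect. The documents do not state the immunohistochemistry scale; a score with few levels would lose less. EBV DNA is the clearest case.

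Stage matters as much as the cut. At 83%/18% and HR 2.0, a stage-stratified median split has 26% power, the same as an unstratified full-scale marker. Without stage, a continuous model could attach a hazard ratio and interval to a confounded signal more often than the split would. This decides the form of the fix.

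A reader might infer three stronger things that the documents do not support.
- That the plan yields no estimate at all: Kaplan-Meier curves do give PFS for each half. What is missing is an estimate and interval between halves.
- That the split makes the trial miss associations that the same data would show: even the full-scale analysis reaches only 26% to 54% power at HR 2.0.
- That every patient will contribute each marker: the study-calendar footnotes in Sections 10.1 and 10.2 request archived slides only where possible.

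**Conclusion.** The point holds as an inexpensive improvement. The small sample justifies avoiding formal tests; it does not justify reducing a quantitative marker to two halves and reporting no between-group estimate.

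For a roughly continuous baseline marker with a log-linear effect, the split costs about 36% of the information. At an assumed HR of 2.0 per SD that is 52% against 36% power with about 13 events, or 26% against 18% with about 9. The gain is small at HR 1.5 and absent for a threshold at the median. These results assume a normal marker, exponential PFS and the historical PFS rates. The simulations used score tests; the penalised interval proposed below was not itself simulated.

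A reader might hope that the change would let the trial rank its markers. It would not: about 11 markers on 7 to 13 events, without multiplicity control, can only generate hypotheses.

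**What to change.** In Section 14.0, items 1a and 2, for baseline EBV DNA (log10) and baseline immunohistochemistry scores, make the stated PFS analysis a Cox model fitted one marker at a time, stratified by stage (I–II against III–IV), with the marker on its continuous or rank scale. Use Firth penalisation because events are few. Report the hazard ratio with a 95% profile-likelihood interval, labelled exploratory, and keep the median-split curves as illustration.

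The text should also state:
- the value substituted for undetectable EBV DNA before taking logs;
- the number of patients with a usable value for each marker;
- that a log-linear effect is assumed and intervals will be wide;
- that about 11 markers are examined without multiplicity control, so the results generate hypotheses and do not rank markers.

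Two parts lie outside this change. Item 1 also concerns "markers of response and resistance through assessment of baseline and on-treatment biopsies", and EBV DNA is sampled serially. Because PFS is counted from treatment start, on-treatment values would need a landmark analysis, so a baseline model does not answer the early-predictor-of-relapse question. Binary mutation data in item 1b need separate handling, since a median cut has no clear meaning for them.

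The cost is SAP wording and a few lines of code, with no new data.

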# 15.0 RESEARCH PARTICIPANT REGISTRATION AND RANDOMIZATION PROCEDURES

#### 15.1 Research Participant Registration

Confirm eligibility as defined in the section entitled Criteria for Patient/Subject Eligibility. Obtain informed consent, by following procedures defined in section entitled Informed Consent Procedures.

During the registration process registering individuals will be required to complete a protocol specific Eligibility Checklist. The individual signing the Eligibility Checklist is confirming whether or not the participant is eligible to enroll in the study.

Study staff is responsible for ensuring that all institutional requirements necessary to enroll a participant to the study have been completed.

See related Clinical Research Policy and Procedure #401 (Protocol Participant Registration): https://one.mskcc.org/sites/pub/clinresearch/Policies/CR%20401.pdf

#### 15.2 Randomization

N/A

#### 16.0 DATA MANAGEMENT ISSUES

This is a multicenter trial that will be coordinated by the Multi-Site Compliance Office at MSK. An MSK Clinical Research Coordinator (CRC) or equivalent at each participating site, will be assigned to the study at each institution. The responsibilities of the MSK CRC include project compliance, data collection, abstraction and entry, data reporting, regulatory monitoring, problem resolution and prioritization, and coordination of the activities of the protocol study team.

The data collected for this study will be entered into a secure database system, Medidata Rave. Source documentation will be available to support the computerized patient record. MSK will be the data coordinating center and will be responsible for reporting to the funding source (as applicable) and governing agencies.

### 16.1 Quality Assurance

Registration reports will be generated to monitor patient accruals and the completeness of registration data. Routine data quality reports will be generated to assess missing data and inconsistencies. Accrual rates and extent and accuracy of evaluations and follow-up will be monitored periodically throughout the study period and potential problems will be brought to the attention of the study team for discussion and action.

Random sample data quality and protocol compliance audits will be conducted by the study team as on ongoing review process.

#### 16.2 Data and Safety Monitoring

The Data and Safety Monitoring (DSM) Plans at Memorial Sloan-Kettering Cancer Center were approved by the National Cancer Institute in September 2001. The plans address the new policies set forth by the NCI in the document entitled "Policy of the National Cancer Institute for Data and Safety Monitoring of Clinical Trials" which can be found at: http://cancertrials.nci.nih.gov/researchers/dsm/index.html.

The DSM Plans at MSKCC were established and are monitored by the MSK Clinical Research Administration Office. The MSKCC Data and Safety Monitoring Plans can be found on the MSKCC Intranet at:

https://one.mskcc.org/sites/pub/clinresearch/Documents/MSKCC Data and Safety Monitoring Plans.pdf

There are several different mechanisms at MSKCC by which clinical trials are monitored for data, safety and quality. There are institutional processes in place for quality assurance (e.g., protocol monitoring, compliance and data verification audits, therapeutic response, and staff education on clinical research QA) and departmental procedures for quality control, plus there are two institutional committees that are responsible for monitoring the activities of our clinical trials programs. The committees: *Data and Safety Monitoring Committee (DSMC)* for Phase I and II clinical trials, and the *Data and Safety Monitoring Board (DSMB)* for Phase III clinical trials, report to the Center's Research Council and Institutional Review Board.

During the protocol development and review process, each protocol will be assessed for its level of risk and degree of monitoring required. Every type of protocol (e.g., NIH sponsored, in-house sponsored, industrial sponsored, NCI cooperative group, etc.) will be addressed and the monitoring procedures will be established at the time of protocol activation.

The MSK DSMC will monitor safety and data quality across all participating institutions (MSK and external sites). Regular study teleconferences with all participating institutions will be held to discuss SAEs or other toxicities and study progress.

Final data sets for publication are required to be locked and stored centrally for potential future access requests from outside entities.

#### 17.0 PROTECTION OF HUMAN SUBJECTS

All the patients will be required to sign an IRB-approved informed consent and will have all their questions fully addressed before enrolling in the study. During informed consent, it will be made clear to the patient that participation is voluntary. All the data will be confidential, maintained in a password protected electronic database and will comply with all HIPAA guidelines.

Every effort will be made to maintain patient confidentiality. Research and hospital records are confidential. Patient's name or any other personally identifying information will not be used in reports or publications resulting from this study. The Food and Drug Administration or other authorized agencies (e.g., qualified monitors) may review patients' records and pathology slides, as required.

#### 17.1 Privacy

MSK's Privacy Office may allow the use and disclosure of protected health information pursuant to a completed and signed Research Authorization form. The use and disclosure of protected health information will be limited to the individuals described in the Research Authorization form. A Research Authorization form must be completed by the Principal Investigator and approved by the IRB and Privacy Board (IRB/PB).

The consent indicates that individualized de identified information collected for the purposes of this study may be shared with other qualified researchers. Only researchers who have received approval from MSK will be allowed to access this information which will not include protected health information, such as the participant's name, except for dates. It is also stated in the Research Authorization that their research data may be shared with other qualified researchers.

### 17.2 Serious Adverse Event (SAE) Reporting

An adverse event is considered serious if it results in ANY of the following outcomes:

- Death
- A life-threatening adverse event
- An adverse event that results in inpatient hospitalization or prolongation of existing hospitalization
- A persistent or significant incapacity or substantial disruption of the ability to conduct normal life functions
- A congenital anomaly/birth defect
- Important Medical Events (IME) that may not result in death, be life threatening, or require hospitalization may be considered serious when, based upon medical judgment, they may jeopardize the patient or subject and may require medical or surgical intervention to prevent one of the outcomes listed in this definition

**Note**: Hospital admission for a planned procedure/disease treatment is not considered an SAE.

SAE reporting is required as soon as the participant starts investigational treatment/intervention. SAE reporting is required for 30-days after the participant's last investigational treatment/intervention. Any event that occur after the 30-day period that is unexpected and at least possibly related to protocol treatment must be reported.

Please note: Any SAE that occurs prior to the start of investigational treatment/intervention and is related to a screening test or procedure (i.e., a screening biopsy) must be reported.

All SAEs must be submitted in PIMS. If an SAE requires submission to the HRPP office per IRB SOP RR-408 'Reporting of Serious Adverse Events', the SAE report must be submitted within 5 calendar days of the event. All other SAEs must be submitted within 30 calendar days of the event.

The report should contain the following information:

- The date the adverse event occurred
- The adverse event
- The grade of the event
- Relationship of the adverse event to the treatment(s)
- If the AE was expected
- Detailed text that includes the following
  - An explanation of how the AE was handled
  - A description of the participant's condition
  - Indication if the participant remains on the study
- If an amendment will need to be made to the protocol and/or consent form
- If the SAE is an Unanticipated Problem

#### For IND/IDE protocols:

The SAE report should be completed as per above instructions. If appropriate, the report will be forwarded to the FDA by the IND Office

### 17.2.1 Merck Global Safety Reporting (MSK ONLY)

For the time period beginning when the consent form is signed until treatment allocation/randomization, any serious adverse event, or follow up to a serious adverse event, including death due to any cause other than progression of the cancer under study that occurs to any subject must be reported **within 2 working days** to Merck Global Safety if it causes the subject to be excluded from the trial, or is the result of a protocol-specified intervention, including but not limited to washout or discontinuation of usual therapy, diet, placebo treatment or a procedure.

For the time period beginning at treatment allocation/randomization through 90 days following cessation of treatment, or 30 days following cessation of treatment if the subject initiates new anticancer therapy, whichever is earlier, any serious adverse event, or follow up to a serious adverse event, including death due to any cause other than progression of the cancer under study whether or not related to the Merck product, must be reported within 2 working days to Merck Global Safety.

Additionally, any serious adverse event, considered by an investigator who is a qualified physician to be related to Merck product that is brought to the attention of the investigator at any time following consent through the end of the specified safety follow-up period specified in the paragraph above, or at any time outside of the time period specified in the previous paragraph also must be reported immediately to the Sponsor and to Merck Global Safety.

All subjects with serious adverse events must be followed up for outcome.

## SAE reports and any other relevant safety information are to be forwarded to the Merck Global Safety [contact]

A copy of all 15 Day Reports and Annual Progress Reports is submitted as required by FDA, European Union (EU), Pharmaceutical and Medical Devices agency (PMDA) or other local regulators. Investigators will cross reference this submission according to local regulations to the Merck Investigational Compound Number (IND, CSA, etc.) at the time of submission.

#### 17.2.2 Events of Clinical Interest

Selected non-serious and serious adverse events are also known as Events of Clinical Interest (ECI) and must be reported within 2 working days to Merck Global Safety. (Attn: Worldwide Product Safety; [contact]).

For the time period beginning when the consent form is signed until treatment allocation/randomization, any ECI, or follow up to an ECI, that occurs to any participant must be reported within 2 working days to Merck Global Safety if it causes the participant to be excluded from the trial, or is the result of a protocol-specified intervention, including but not limited to washout or discontinuation of usual therapy, diet, placebo treatment or a procedure.

For the time period beginning at treatment allocation/randomization through 90 days following cessation of treatment, or 30 days following cessation of treatment if the participant initiates new anticancer therapy, whichever is earlier, any ECI, or follow up to an ECI, whether or not related to Merck product, must be reported within 2 working days to Merck Global Safety.

Events of clinical interest for this trial include:

- 1. an overdose of Merck product, as defined in Section 17.2.3 Definition of an Overdose for This Protocol and Reporting of Overdose to the Sponsor, that is not associated with clinical symptoms or abnormal laboratory results.
- 2. an elevated AST or ALT lab value that is greater than or equal to 3X the upper limit of normal and an elevated total bilirubin lab value that is greater than or equal to 2X the upper limit of normal and, at the same time, an alkaline phosphatase lab value that is less than 2X the upper limit of normal, as determined by way of protocol-specified laboratory testing or unscheduled laboratory testing.\*

\*Note: These criteria are based upon available regulatory guidance documents. The purpose of the criteria is to specify a threshold of abnormal hepatic tests that may require an additional evaluation for an underlying etiology.

